Telemedicine has emerged as a valuable tool in diabetes management, especially through remote monitoring, communication platforms, and therapeutic adjustments. However, most studies involving telemedicine focus on outpatient or primary care contexts.

Given the severity of diabetes-related complications, the economic impact of hospitalizations, the persistently high readmission rates, and the need to strengthen medical knowledge for inpatient diabetes care, this study proposes a structured, telemedicine-based educational intervention. The objective is to evaluate its effectiveness in improving medical knowledge, insulin prescription quality, and the prevention and management of glycemic extremes during hospitalization.

2. Primary and Secondary Objectives

Primary objective:

To evaluate the impact of a structured educational intervention via telemedicine on internal medicine residents' knowledge regarding inpatient hyperglycemias.

Secondary objectives:

To assess the effect of the intervention on the quality of insulin prescriptions and capillary blood glucose monitoring.

To evaluate the effect on the occurrence of hypoglycemia and hyperglycemia during hospitalization.

To compare the length of hospital stay between the intervention and control groups.

3. Study Design

This was an open-label, multicenter, randomized clinical trial conducted at university hospitals located in southern Brazil. Internal medicine clinical teams were block-randomized using stratified allocation by center to ensure balance between groups.

The intervention group received a 30-minute online theoretical lecture on hospital hyperglycemia and participated in a 30-day telemedicine-based continuing education program delivered via a messaging platform. The control group continued standard clinical activities without any educational intervention.

Data collection occurred in two phases: a pre-post knowledge assessment using a validated questionnaire, and a retrospective chart review of hospitalized patients cared for by the participating teams.

4. Intervention

Residents in the intervention group received a 30-minute online theoretical lecture on inpatient hyperglycemia, followed by daily educational content for 30 days via a messaging application. Materials included short videos, texts, and clinical guidance on diabetes and hospital glycemic management.

The control group received no educational content and maintained routine clinical duties.

5. Inclusion and Exclusion Criteria

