Inclusion criteria:

Internal medicine residents assigned to clinical teams at participating hospitals.

Exclusion criteria:

Residents on leave during the intervention period.

Teams supervised by endocrinologists.

Residents who declined participation.

6. Outcome Measures (Primary and Secondary)

Primary outcome:

Change in medical knowledge on inpatient hyperglycemia, assessed through a validated questionnaire before and after the intervention.

Secondary outcomes:

Quality of glucose monitoring and insulin prescribing.

Incidence of hyperglycemia (>180 mg/dL) and hypoglycemia (<70 mg/dL).

Length of hospital stay

7. Sample Size Calculation

Based on previous data showing 46.44% accuracy in key knowledge items, and assuming an increase to 80% after the intervention, with 80% power and a 5% significance level, a minimum of 62 completed questionnaires (including both pre- and post-intervention assessments) was required.

8. Statistical Analysis Plan

Categorical variables were described as frequencies and percentages. Continuous variables were expressed as means and standard deviations or medians and interquartile ranges, based on normality (Shapiro-Wilk test).

Between-group comparisons were made using Student's t-test or the Mann-Whitney U test for continuous variables, depending on distribution. Categorical variables were analyzed using Pearson's chi-square test or Fisher's exact test, as appropriate. Logistic regression analysis was performed to identify independent predictors, including variables with clinical relevance or $p < 0.20$ in the univariate analysis. Statistical analyses were conducted using IBM SPSS Statistics for Windows, Version 29.0 (IBM Corp., Armonk, NY, USA). A two-sided p -value < 0.05 was considered statistically significant.

9. Ethical Considerations

All participating physicians provided informed consent. Data were collected with institutional authorization and approval by the local ethics committee. Confidentiality and privacy were strictly maintained for all participants and patient information.

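### For the primary knowledge outcome, Section 8 names only unadjusted comparisons: baseline knowledge is collected but not named as a covariate, which can cost precision if the outcome is a continuous score

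*Combined protocol and SAP*

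**What the plan says.** All references are to the combined protocol and SAP.

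- Section 6 defines the primary outcome as "Change in medical knowledge on inpatient hyperglycemia, assessed through a validated questionnaire before and after the intervention". Section 3 describes "a pre-post knowledge assessment using a validated questionnaire", so a baseline measure of the outcome exists by design.
- Section 3 also states: "Internal medicine clinical teams were block-randomized using stratified allocation by center to ensure balance between groups".
- Section 8 gives Student's t-test or "the Mann-Whitney U test for continuous variables, depending on distribution" for continuous variables, chosen by Shapiro-Wilk. For the rest: "Categorical variables were analyzed using Pearson's chi-square test or Fisher's exact test, as appropriate".
- The only model is in Section 8: "Logistic regression analysis was performed to identify independent predictors". It names no outcome, no arm term and no baseline score.
- Section 7 says that "a minimum of 62 completed questionnaires (including both pre- and post-intervention assessments) was required". It plans on a proportion correct, 46.44% rising to 80%.

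The documents do not say whether knowledge is analysed as a score per resident or as right/wrong items, or whether the t-test is applied to the change or to the post-intervention score. They give no number of teams or centres.

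**The concern.** A pre-intervention score on the same questionnaire is normally the strongest predictor of the post-intervention score. None of the four listed tests can use it as a covariate. At best it enters by subtraction, which fixes its coefficient at 1 whatever the data show. Centre, the stratification factor, is not used either, and no listed test recognises that residents were allocated by team.

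What is at stake for baseline is the width of the confidence interval for the primary outcome in a small trial. The point is confined to that outcome and to a continuous score per resident, including percent correct. It does not extend to the chart-review outcomes.

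**Working it through.** **Inputs.** From the documents: knowledge measured before and after; teams randomised within centre; 46.44% and 80%; 80% power; two-sided 5%; 62 questionnaires. Not in the documents, so assumed: pre-post correlation r, the ratio of pre to post SD, the intra-team correlation (ICC), the SD between centres, 3 centres, and the number and size of teams.

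**1. The plan's own figure.** Two-sided arcsine formula: h = 2·arcsin√0.80 − 2·arcsin√0.4644 = 0.715, and n = 2(1.960 + 0.842)²/h² = 30.7, so 31 per group and 62 in all. The pooled two-proportion formula gives 32 per group, 64 in all. The figure reproduces and is not at issue here.

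**2. Independent residents, equal SDs (s).** The variance factor is 2s²(1 − r) for a change score and s²(1 − r²) with baseline as covariate (ANCOVA). The ratio is (1 + r)/2, and the CI shortens by 1 − √ratio.

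| r | Variance ratio | CI shorter by |
|---|---|---|
| 0.3 | 0.65 | 19.4% |
| 0.5 | 0.75 | 13.4% |
| 0.7 | 0.85 | 7.8% |
| 0.9 | 0.95 | 2.5% |

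With k = SD pre / SD post, the ratio is (1 − r²)/(1 + k² − 2rk). It equals 1 when k = r; at r = 0.7 and k = 0.75 it is 0.51/0.5125 = 0.995, so almost nothing is gained. If the t-test is applied to the post score alone, the ratio is 1 − r²: 0.91, 0.75 and 0.51 at r = 0.3, 0.5 and 0.7.

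**3. Team-level inference on both sides.** By simulation, arms are compared with a t interval on team values: either mean change, or mean post score minus b times mean baseline score, with b the pooled within-team slope. ICC is 0.1 and centre SD 0.3 unless stated. Widths are in SD units.

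*Differences not carried over.* Centre effects enter the post score only, and team effects in the residual are independent of those at baseline. Mean CI width, change to adjusted:

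| r | 12 teams of 5, centre included | 6 teams of 10, no centre term |
|---|---|---|
| 0.3 | 1.61 to 1.32 | 2.54 to 2.19 |
| 0.5 | 1.36 to 1.19 | 2.23 to 2.05 |
| 0.7 | 1.06 to 0.99 | 1.91 to 1.83 |
| 0.9 | 0.61 to 0.60 | 1.49 to 1.48 |

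*Differences stable from pre to post* (r now within team, r = 0.5):

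| Layout | Change | Adjusted |
|---|---|---|
| 6 teams of 10, no centre term, ICC 0.1 | 1.28 | 1.44 |
| 12 teams of 5, centre included, ICC 0.1 | 1.09 | 1.05 |
| 12 teams of 5, centre included, ICC 0.2 | 1.03 | 1.07 |

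The reversal has a simple cause. A change score removes a persistent difference entirely; adjustment leaves a fraction 1 − b of it. For 6 teams of 10, the variance of a team value is 2(0.5)(0.9)/10 = 0.090 for change. Adjusted, it is (0.75)(0.9)/10 + 0.5²(0.1 + 0.3²) = 0.115. √(0.115/0.090) = 1.13, in line with 1.44/1.28 = 1.125.

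**4. Team is a separate matter.** In the first scenario, with 12 teams of 5 and r = 0.5, a resident-level change t-test has type I error 6.2%, 9.5% and 13.3% at ICC 0.05, 0.1 and 0.2. Resident-level ANCOVA with centre has 7.2%, 10.6% and 14.7%. Adding baseline and centre does not cure this.

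**5. Centre.** Baseline-adjusted CI width without/with centre, first scenario, r = 0.5, at centre SD 0.1, 0.3 and 0.5. For 12 teams: 1.18/1.19, 1.33/1.19, 1.59/1.20. For 6 teams: 1.68/2.37, 2.05/2.37, 2.64/2.37. With 6 teams in 3 centres, the centre term leaves 2 degrees of freedom (critical t 4.303) instead of 4 (2.776).

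**The case against.** The strongest objection is that the outcome is defined as a change, so a t-test on change matches the definition and already uses baseline. Moreover, if teams and centres differ persistently in knowledge, change is the better estimator. The second part stands: in that case the adjusted interval was wider in two of the three layouts in step 3, and nothing in the documents shows which scenario applies. The first part stands only in part. Adjusting for baseline estimates the same arm difference, and Section 8 does not say that its test is applied to change.

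The only evidence on scale is the proportion in Section 7. If right/wrong items are the unit of analysis, the variance formulas do not apply and no gain is claimed. The logistic regression could admit baseline knowledge under its clinical-relevance rule, so the accurate statement is that baseline is not named. That model is not presented as a group comparison, however, and could not analyse a continuous score.

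A reader might infer more: that the unadjusted comparison is biased, that adjustment always shortens the interval, or that baseline adjustment would repair the neglect of team. The documents support none of these. Under randomisation, leaving out baseline or centre does not in itself bias the comparison or inflate type I error. Step 3 shows that the gain is conditional, and step 4 that the team problem remains.

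**Conclusion.** The point holds as a matter of efficiency. For the primary knowledge outcome the plan names no baseline-adjusted comparison and none that accounts for team. For a continuous score per resident, independent residents and equal SDs, the CI would be about 3% to 19% shorter with adjustment than with a change score for r from 0.9 down to 0.3. With team-level inference, and differences that do not carry over, the reduction is similar or smaller: 1.36 to 1.19 SD for 12 teams of 5 at r = 0.5. With stable team and centre differences the result at r = 0.5 runs from a small gain (1.09 to 1.05) to a loss of about 12.5% (1.28 to 1.44). Every one of these sizes rests on assumed values of r, ICC, centre SD and team layout. Confidence is medium because the outcome scale is not stated.

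**What to change.** Add one paragraph to Section 8:

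- Name a single primary analysis for a continuous score: post-intervention score on arm and the resident's baseline score, with inference at team level. Choose in advance either team-level summaries or a random team intercept, with small-sample degrees of freedom based on the number of teams.
- Report the adjusted mean difference with its 95% CI whatever the Shapiro-Wilk result.
- State the team-level change-score comparison as a sensitivity analysis.
- Decide on centre in advance from the number of teams, including it when teams are numerous relative to centres. Any numeric cut-off, such as 8 residual degrees of freedom, is a convention and is not derived from the documents.
- If right/wrong items are the outcome, say so and name the model and effect measure separately.

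The costs are real. Pre and post forms must be linked by resident, which the documents do not confirm. Team-level degrees of freedom are few: 8 (critical t 2.306) for 12 teams in 3 centres with centre, 4 for 6 teams without it. That is the price of handling team, not of adjusting for baseline. There may be a modest loss against change if team and centre differences are stable. The document is written in the past tense; if the data have already been analysed, the new analysis must be labelled post hoc.

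### Section 8 plans no between-arm effect estimate or confidence interval for any outcome, so a non-significant hypoglycaemia test could not by itself rule out an increase

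*Combined protocol and SAP*

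**What the plan says.** Section 2 sets a secondary objective: "To evaluate the effect on the occurrence of hypoglycemia and hyperglycemia during hospitalization". Section 6 lists the matching outcome as "Incidence of hyperglycemia (>180 mg/dL) and hypoglycemia (<70 mg/dL".

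Section 8 has four relevant parts:

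- Description: "Categorical variables were described as frequencies and percentages". Continuous variables get means or medians with their spread.
- Testing: "Categorical variables were analyzed using Pearson's chi-square test or Fisher's exact test, as appropriate". Continuous variables get Student's t-test or Mann-Whitney.
- Modelling: "Logistic regression analysis was performed to identify independent predictors, including variables with clinical relevance", or a univariate p below 0.20. The dependent variable is not named, and no odds ratio or interval is promised.
- Threshold: "A two-sided p -value < 0.05 was considered statistically significant".

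Section 3 says that clinical teams, not patients, were randomised, stratified by centre, and that patient data come from a retrospective chart review. Section 7 sizes the study on questionnaire accuracy alone.

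**The concern.** The objective asks how much the intervention changed glucose events. The planned analysis answers only whether a difference crosses a threshold. Chi-square, Fisher and Mann-Whitney tests do not in themselves give an effect size or its precision.

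The gap applies to every outcome, but hypoglycaemia shows it most clearly. Section 1 links glycaemic disturbances, hypoglycaemia included, to longer stays, morbidity and mortality, so readers will want to know whether it rose or fell. If the test is non-significant, the plan provides nothing that separates a precise result near zero from an imprecise one that leaves room for a sizeable rise.

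The tests also assume independent observations. Patients share a team, and the team is what was randomised. An interval that a reader rebuilt from the reported percentages would have the same fault.

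**Working it through.** **The plan's own figure.** Section 7 gives 46.44% against 80%, "with 80% power and a 5% significance level", and 62 questionnaires. Treat these as two independent groups of equal size (the document does not state the split).

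- Pooled formula: n = [1.96·√(2·0.6322·0.3678) + 0.8416·√(0.4644·0.5356 + 0.80·0.20)]² / 0.3356² = (1.3366 + 0.5381)² / 0.1126 = 31.2, so 32 per group and 64 in total.
- Arcsine formula: n = 2·(1.96 + 0.8416)² / 0.7148² = 30.7, so 31 per group and 62 in total.

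The 62 is therefore reproduced, but it concerns knowledge only. It gives no assurance about precision for hypoglycaemia.

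**Assumptions for hypoglycaemia.** The documents give no chart count, event rate, number of teams or intracluster correlation. I assume one yes/no outcome per patient chart, n charts per arm, the same rate p in both arms, and a design effect (DE) of 1 or 2 for teams.

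**Precision.** The 95% half-width of the risk difference is 1.96·√(2·p·(1−p)·DE/n).

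| n per arm | p | DE | Half-width (points) |
|---|---|---|---|
| 150 | 10% | 1 | 1.96·√(0.18/150) = 6.8 |
| 300 | 10% | 1 | 1.96·√(0.18/300) = 4.8 |
| 150 | 10% | 2 | 1.96·√(0.36/150) = 9.6 |
| 300 | 10% | 2 | 1.96·√(0.36/300) = 6.8 |
| 400 | 5% | 1 | 1.96·√(0.095/400) = 3.0 |
| 100 | 20% | 2 | 1.96·√(0.64/100) = 15.7 |

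The last two rows are the extremes over 100 to 400 charts per arm and rates of 5% to 20%. With 150 charts per arm and 10% observed in both arms, the upper limit for the difference is +6.8 points, or +9.6 with DE 2.

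**A non-significant example.** Take 16 of 100 against 10 of 100. Chi-square gives p = 0.21 and Fisher p = 0.29. The difference is +6 points, with standard error √(0.16·0.84/100 + 0.10·0.90/100) = 0.0474, so the 95% interval is −3.3 to +15.3 points. The p-value alone does not show that upper limit. This calculation ignores clustering, and allowing for positive within-team correlation would widen it.

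**Power to detect a doubling.** Power = Φ{[|p₂−p₁|·√(n/DE) − 1.96·√(2·p̄·(1−p̄))] / √(p₁(1−p₁) + p₂(1−p₂))}, where p̄ is the mean of the two rates.

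- 100 per arm, 10% to 20%: 51%, or 29% with DE 2.
- 100 per arm, 5% to 10%, DE 2: 15%.
- 400 per arm, 20% to 40%, DE 1: above 99%.

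How much a non-significant result would mean depends on quantities that the documents do not give.

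**The case against.** Several points on the other side are fair.

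- **The percentages by arm will be reported.** A reader can subtract them, and the t-test rests on a mean difference. That stands, so the plan is not wholly without information on effects. But Section 8 commits to no interval, and one rebuilt from the percentages would ignore the teams.
- **Logistic regression could give an odds ratio.** It could, but no dependent variable is named, it is aimed at finding predictors, and covariates may enter by univariate p-value. It is not a planned estimate of the treatment effect.
- **The outcome may not be binary per patient.** Section 6 does not say whether incidence counts patients, readings or patient-days. The figures above assume patients. The absence of an estimate and interval does not depend on that choice.
- **The chart count is unknown.** With many charts and a common event, a doubling would be detected almost surely. That limits any claim about size, but an interval shows the precision whatever the count turns out to be.

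A reader might also infer that hypoglycaemia is the expected harm of heavier insulin use and that the trial would present a non-significant result as safe. The documents support neither. Nothing in them says that the intervention increases insulin use. Section 2 frames the aim as benefit: "improving medical knowledge, insulin prescription quality, and the prevention and management of glycemic extremes during hospitalization". There is no safety or non-inferiority objective, and Section 8 does not say how a non-significant result will be read.

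**Conclusion.** The concern holds as a general gap in Section 8: no between-arm estimate or confidence interval is specified for any outcome, and the listed tests ignore the randomised unit. For hypoglycaemia, a non-significant test alone could not exclude an increase. It does not follow that the trial intends to claim safety.

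The size is conditional. The half-width is 4.8 to 6.8 points under a 10% rate with 300 to 150 charts per arm, and 6.8 to 9.6 with a design effect of 2. Across the wider assumed range it is about 3 to 16 points. All of this rests on assumed rates, chart counts and design effects, and on a patient-level binary outcome. The change is worth making because the stated objective asks for an effect and the remedy is cheap. These are secondary outcomes, so the gap does not undermine the trial as a whole.

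**What to change.** In Section 8, make the between-arm difference with its 95% confidence interval the reported result for each outcome, with the p-value alongside:

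- Risk difference or risk ratio for binary outcomes (glucose events and binary quality measures), after stating the unit in which incidence is counted.
- Mean difference for knowledge and for length of stay.
- Standard errors that account for the randomised team and the centre strata. If teams are few, use a method suited to a small number of clusters.
- A sentence saying that hypoglycaemia will be interpreted from both limits of its interval, and that p>0.05 will not be taken as evidence of no increase.
- The number of teams and charts per arm, so that readers can judge precision.

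The cost is some SAP wording and minor extra analysis of data already collected. Intervals that respect the team will probably be wider than naive ones. The document is written in the past tense, so the change should be dated and described as an addition to the plan.

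### No analysis in section 8 has to give an intervention effect that uses centre and allows for team, the unit that was randomised

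*Combined protocol and SAP*

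**What the plan says.** Section 3 (Study Design) sets the randomised unit and the stratum: "Internal medicine clinical teams were block-randomized using stratified allocation by center to ensure balance between groups". It also says that the second data source is "a retrospective chart review of hospitalized patients cared for by the participating teams". Patients are therefore grouped by randomised team, and teams by centre.

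Section 2 (Primary and Secondary Objectives) asks for intervention effects, for example "To evaluate the effect on the occurrence of hypoglycemia and hyperglycemia during hospitalization" and "To compare the length of hospital stay between the intervention and control groups".

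Section 8 (Statistical Analysis Plan) answers with two kinds of analysis:

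- Unadjusted tests. For continuous variables: "Between-group comparisons were made using Student's t-test or the Mann-Whitney U test for continuous variables, depending on distribution". For categorical variables: Pearson chi-square or Fisher's exact test.
- One adjusted model: "Logistic regression analysis was performed to identify independent predictors, including variables with clinical relevance or $p < 0.20$ in the univariate analysis".

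The threshold for all of them is the same: "A two-sided p -value < 0.05 was considered statistically significant". The documents contain no mixed model, GEE, cluster-robust variance, stratified test or team-level analysis. The logistic model has no named dependent variable, no candidate list and no terms that must be included, and clinical relevance is not defined.

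**The concern.** When teams are randomised and patients of the same team resemble each other, the information about arm depends on the number of teams as well as the number of patients. A test that treats patients as independent gives a standard error for the arm effect that is too small, so chance differences between teams can be read as an effect of the education. This applies equally to the t-test, the Mann-Whitney test, the chi-square test and a logistic model without team.

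The adjusted model does not repair this. Nothing obliges it to contain arm, centre or team. Its form is logistic, so it gives no adjusted effect for length of stay or for a knowledge score unless these are dichotomised, which the plan does not say. At stake are the claims on prescribing quality, hypo- and hyperglycaemia and length of stay. The knowledge comparison is affected to a smaller degree, since residents also belong to teams.

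**Working it through.** **1. The plan's own figure.** Section 7 states "a minimum of 62 completed questionnaires (including both pre- and post-intervention assessments) was required", from 46.44% versus 80%, 80% power and 5% significance. The two-sided arcsine formula for two independent groups uses h = 2·arcsin√0.80 − 2·arcsin√0.4644 = 0.715. Then n = 2·[(1.960 + 0.842)/0.715]² = 30.7, so 31 per group and 62 in total. The pooled normal formula gives 32 per group, 64 in total. The figure of 62 thus reproduces as a calculation for independent observations, with no allowance for team.

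**2. Inputs that must be assumed.** The documents give no number of teams, centres or patients and no ICC. Assumed: 8, 12 or 20 teams; 10, 17 or 25 patients per team; 2 centres with event rates of 30% and 40%; ICC 0 to 0.10.

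**3. Formula check.** Design effect DE = 1 + (m − 1)·ICC. The standard error is too small by a factor √DE, and the actual error of a nominal 5% test is about 2·[1 − Φ(1.96/√DE)].

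| m | ICC | DE | √DE | actual error |
|---|---|---|---|---|
| 10 | 0.02 | 1 + 9×0.02 = 1.18 | 1.09 | 7.1% |
| 17 | 0.05 | 1 + 16×0.05 = 1.80 | 1.34 | 14.4% |
| 25 | 0.10 | 1 + 24×0.10 = 3.40 | 1.84 | 28.8% |

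**4. Simulation, binary outcome, no arm effect** (beta-binomial, teams 1:1 within centre, 20,000 replicates). Share of datasets with p<0.05 for arm:

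| ICC | logistic, arm + centre, no team |
|---|---|
| 0 | 4.7%-5.0% |
| 0.02 | 6.9%-10.6% |
| 0.05 | 10.2%-19.0% |
| 0.10 | 15.6%-29.7% |

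The unadjusted chi-square test behaves almost identically, at about 7% to 30% over ICC 0.02-0.10. Regression of team proportions on arm and centre, with a t reference on (teams − 3) degrees of freedom, stays at 4.7%-5.6%. Requiring arm to pass p<0.20 first changes the logistic figures by no more than 0.1 point, so the screen is not the source of the excess.

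**5. Continuous outcome, such as length of stay** (same design, five of the team-size settings, 10,000 replicates, ICC 0.02-0.10): 6.9%-29.4% with team ignored, 4.7%-5.5% with team means.

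**6. Knowledge.** By the formula in step 3, with an assumed 3 to 5 residents per team, the actual error is about 6.2% (m = 3, ICC 0.05), 7.4% (m = 5, ICC 0.05) and 9.8% (m = 5, ICC 0.10).

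**7. The screen on its own.** Suppose, contrary to the text, that p<0.20 were the only route into the model. Full binomial enumeration with the Pearson chi-square test at 46.44% versus 80% gives the chance that arm is left out. It is 5.5% with 31 per arm. If the 62 forms count pre and post together and half are post, it is 23.0%-24.6% with 15 and 16 per arm. For null covariates, the error per candidate with the screen is 1%-5%. With 10 candidates, at least one false predictor appears in 10%-38% of datasets with the screen and in 40%-45% if all are fitted.

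**The case against.** The strongest reply is that the logistic model is declared as a search for predictors, that the intervention is tested by the between-group comparisons, and that those do not depend on how the search picks its variables. Most of this stands. A reader might infer that the plan guarantees no intervention comparison at all; it does provide unadjusted ones. What they lack is any use of centre and a standard error that reflects randomisation by team, and the only adjusted model is not required to supply either.

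A reader might also infer that the p<0.20 rule is likely to drop arm or to inflate false findings. The documents do not support this. Entry is also allowed for clinical relevance, and arm is the variable that the trial exists to test, so it would probably enter. The drop-out figures in step 7 describe a rule that the plan does not state, and they depend on how the 62 is read. The screen does not raise the error per candidate above 5%, and it lowers the number of false predictors compared with fitting everything.

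Finally, the size rests on assumed settings. That is correct: at ICC 0.02 with 10 patients per team the error is only about 7%, and the value near 30% needs ICC 0.10 with 25 per team. At ICC 0 there is no excess. No separate size is claimed for leaving out centre.

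**Conclusion.** The point holds as a gap in all of section 8. Teams were randomised within centre, yet no planned analysis must give an arm effect that uses centre and allows for team. That much follows from the text and needs no assumed number. Its size does: with 8-20 teams of 10-25 patients, 2 centres and ICC 0.02-0.10, a null arm effect is declared significant in about 7%-30% of datasets, against about 5% with a team-level analysis. The excess comes from ignoring team, in the unadjusted tests as much as in the logistic model. The undefined entry rule and the unnamed outcome are minor points of specification. The change should be made; confidence in the size is medium, because the real team counts, team sizes and ICC are not in the documents.

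**What to change.** In section 8, for each outcome, name one intervention-effect analysis that:

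- always includes arm and centre, with at most a short baseline covariate list fixed in advance;
- allows for team: team-level regression on arm and centre if teams are few, otherwise a random team effect or GEE with a small-sample correction;
- reports the arm effect with its 95% CI: an odds ratio for binary outcomes (a difference in proportions for a team-level model), and the analogous adjusted difference for length of stay and knowledge score.

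State the numbers of teams and centres. Keep the logistic predictor search as exploratory, with its outcome named and no significance claims. Do not merely delete the p<0.20 clause and fit every candidate, because step 7 shows that this gives more false predictors.

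Cost: one refit per outcome with data already held, provided that team and centre were recorded. Intervals for arm will widen; in the assumed settings standard errors rise by about 9% (√1.18 = 1.09) to 84% (√3.40 = 1.84). Claims of confirmed independent predictors are given up. Section 8 is written in the past tense, so if outcomes have already been analysed the new model must be disclosed as post hoc.
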